7.2.3.2 Events of Clinical Interest

Selected non-serious and serious adverse events are also known as Events of Clinical Interest (ECI) and must be reported to the Sponsor.

For the time period beginning when the consent form is signed until treatment allocation/randomization, any ECI, or follow up to an ECI, that occurs to any subject must be reported within 24 hours to the Sponsor if it causes the subject to be excluded from the trial, or is the result of a protocol-specified intervention, including but not limited to washout or discontinuation of usual therapy, diet, placebo treatment or a procedure.

For the time period beginning at treatment allocation/randomization through 30 days following cessation of treatment, any ECI, or follow up to an ECI, whether or not related to the Sponsor's product, must be reported within 24 hours to the Sponsor, either by electronic media or paper. Electronic reporting procedures can be found in the EDC data entry guidelines. Paper reporting procedures can be found in the Investigator Trial File Binder (or equivalent).

Events of clinical interest for this trial include:

1. an overdose of Sponsor's product, as defined in Section 7.2.1 - Definition of an Overdose for This Protocol and Reporting of Overdose to the Sponsor, that is not associated with clinical symptoms or abnormal laboratory results.
2. an elevated AST or ALT lab value that is greater than or equal to 3X the upper limit of normal and an elevated total bilirubin lab value that is greater than or equal to 2X the upper limit of normal and, at the same time, an alkaline phosphatase lab value that is less than 2X the upper limit of normal, as determined by way of protocol-specified laboratory testing or unscheduled laboratory testing.*

*Note: These criteria are based upon available regulatory guidance documents. The purpose of the criteria is to specify a threshold of abnormal hepatic tests that may require an additional evaluation for an underlying etiology. The trial site guidance for assessment and follow up of these criteria can be found in the Investigator Trial File Binder (or equivalent).

7.2.3.2.1 Follow-Up Post-Allogeneic Stem Cell Transplantation

For subjects who have an allogeneic SCT within 24 months of last dose of pembrolizumab or before the end of the trial, transplant parameters will be collected, and specific ECIs will be collected for 18 months from the date of the allogeneic transplant, to include graft-versus-host-disease, hepatic veno-occlusive disease and/or sinusoidal syndrome, febrile syndrome (a steroid-requiring febrile illness without an infectious cause), pulmonary complications, immune-mediated AEs, critical illness, and transplant-related mortality for all grades, and regardless of relationship to trial drug. Additional medically important AEs post-allogeneic SCT may be submitted at the investigator's discretion.

Post-allogeneic SCT events of ECIs that occur after the normal safety follow-up period and before the end of the trial must be assessed for seriousness and causality and reported to the sponsor as follows: within 24 hours if serious regardless of causality or if non-serious and considered to be drug related; and 5 calendar days if non-serious and not considered to be drug related.

Guidance on details to be collected and suggested events to be reported can be found in the Procedure Manual.

7.2.3.3 Protocol-Specific Exceptions to Serious Adverse Event Reporting

Efficacy endpoints as outlined in this section will not be reported to the Sponsor as described in Section 7.2.3, Immediate Reporting of Adverse Events to the Sponsor.

Specifically, the suspected/actual events covered in this exception include any event that is disease progression of the cancer under trial.

The Sponsor will monitor unblinded aggregated efficacy endpoint events and safety data to ensure the safety of the subjects in the trial. Any suspected endpoint which upon review is not progression of the cancer under trial will be forwarded to global safety as a SAE within 24 hours of determination that the event is not progression of the cancer under trial.

7.2.4 Evaluating Adverse Events

An investigator who is a qualified physician will evaluate all adverse events according to the NCI Common Terminology for Adverse Events (CTCAE), version 4.0. Any adverse event which changes CTCAE grade over the course of a given episode will have each change of grade recorded on the adverse event case report forms/worksheets.

All adverse events regardless of CTCAE grade must also be evaluated for seriousness.

For studies in which multiple agents are administered as part of a combination regimen, the investigator may attribute each adverse event causality to the combination regimen or to a single agent of the combination. In general, causality attribution should be assigned to the combination regimen (i.e., to all agents in the regimen). However, causality attribution may be assigned to a single agent if in the investigator's opinion, there is sufficient data to support full attribution of the adverse experience to the single agent.

Table 17 Evaluating Adverse Events

An investigator who is a qualified physician, will evaluate all adverse events as to:

V4.0 CTCAE Grading	Grade 1	Mild; asymptomatic or mild symptoms; clinical or diagnostic observations only; intervention not indicated.
	Grade 2	Moderate; minimal, local or noninvasive intervention indicated; limiting age-appropriate instrumental ADL.
	Grade 3	Severe or medically significant but not immediately life-threatening; hospitalization or prolongation or hospitalization indicated; disabling; limiting self-care ADL.
	Grade 4	Life threatening consequences; urgent intervention indicated.
	Grade 5	Death related to AE
Seriousness	A serious adverse event is any adverse event occurring at any dose or during any use of Sponsor's product that:	
	† Results in death; or	
	† Is life threatening; or places the subject, in the view of the investigator, at immediate risk of death from the event as it occurred (Note: This does not include an adverse event that, had it occurred in a more severe form, might have caused death.); or	
	† Results in a persistent or significant disability/incapacity (substantial disruption of one's ability to conduct normal life functions); or	
	† Results in or prolongs an existing inpatient hospitalization (hospitalization is defined as an inpatient admission, regardless of length of stay, even if the hospitalization is a precautionary measure for continued observation. (Note: Hospitalization for an elective procedure to treat a pre-existing condition that has not worsened is not a serious adverse event. A pre-existing condition is a clinical condition that is diagnosed prior to the use of a Merck product and is documented in the patient's medical history.); or	
	† Is a congenital anomaly/birth defect (in offspring of subject taking the product regardless of time to diagnosis); or	
	Is a new cancer (that is not a condition of the study) (although not serious per ICH definition, is reportable to the Sponsor within 24 hours to meet certain local requirements); or	
	Is an overdose (whether accidental or intentional). Any adverse event associated with an overdose is considered a serious adverse event for collection purposes. An overdose that is not associated with an adverse event is considered a non-serious event of clinical interest and must be reported within 24 hours.	
	Other important medical events that may not result in death, not be life threatening, or not require hospitalization may be considered a serious adverse event when, based upon appropriate medical judgment, the event may jeopardize the subject and may require medical or surgical intervention to prevent one of the outcomes listed previously (designated above by a †).	
Duration	Record the start and stop dates of the adverse event. If less than 1 day, indicate the appropriate length of time and units	
Action taken	Did the adverse event cause the Sponsor's product to be discontinued?	

Relationship to Sponsor's Product	
Did the Sponsor's product cause the adverse event? The determination of the likelihood that the Sponsor's product caused the adverse event will be provided by an investigator who is a qualified physician. The investigator's signed/dated initials on the source document or worksheet that supports the causality noted on the AE form, ensures that a medically qualified assessment of causality was done. This initialed document must be retained for the required regulatory time frame. The criteria below are intended as reference guidelines to assist the investigator in assessing the likelihood of a relationship between the test drug and the adverse event based upon the available information.
 
The following components are to be used to assess the relationship between the Sponsor's product and the AE; the greater the correlation with the components and their respective elements (in number and/or intensity), the more likely the Sponsor's product caused the adverse event (AE):
	
	Exposure	Is there evidence that the subject was actually exposed to the Sponsor's product such as: reliable history, acceptable compliance assessment (pill count, diary, etc.), expected pharmacologic effect, or measurement of drug/metabolite in bodily specimen?
	Time Course	Did the AE follow in a reasonable temporal sequence from administration of the Sponsor's product? Is the time of onset of the AE compatible with a drug-induced effect (applies to trials with investigational medicinal product)?
	Likely Cause	Is the AE not reasonably explained by another etiology such as underlying disease, other drug(s)/vaccine(s), or other host or environmental factors
Relationship to Sponsor's Product (continued)	The following components are to be used to assess the relationship between the test drug and the AE: (continued)	
	Dechallenge	
Was the Sponsor's product discontinued or dose/exposure/frequency reduced? If yes, did the AE resolve or improve? If yes, this is a positive dechallenge. If no, this is a negative dechallenge. (Note: This criterion is not applicable if: (1) the AE resulted in death or permanent disability; (2) the AE resolved/improved despite continuation of the Sponsor's product; or (3) the trial is a single-dose drug trial); or (4) Sponsor's product(s) is/are only used one time.)

	Rechallenge	
Was the subject re-exposed to the Sponsor's product in this study? If yes, did the AE recur or worsen? If yes, this is a positive rechallenge. If no, this is a negative rechallenge. (Note: This criterion is not applicable if: (1) the initial AE resulted in death or permanent disability, or (2) the trial is a single-dose drug trial); or (3) Sponsor's product(s) is/are used only one time). NOTE: IF A RECHALLENGE IS PLANNED FOR AN ADVERSE EVENT WHICH WAS SERIOUS AND WHICH MAY HAVE BEEN CAUSED BY THE SPONSOR'S PRODUCT, OR IF REEXPOSURE TO THE SPONSOR'S PRODUCT POSES ADDITIONAL POTENTIAL SIGNIFICANT RISK TO THE SUBJECT, THEN THE RECHALLENGE MUST BE APPROVED IN ADVANCE BY THE SPONSOR CLINICAL DIRECTOR AS PER DOSE MODIFICATION GUIDELINES IN THE PROTOCOL.

	Consistency with Trial Treatment Profile	Is the clinical/pathological presentation of the AE consistent with previous knowledge regarding the Sponsor's product or drug class pharmacology or toxicology?

The assessment of relationship will be reported on the case report forms /worksheets by an investigator who is a qualified physician according to his/her best clinical judgment, including consideration of the above elements.
		

Record one of the following	Use the following scale of criteria as guidance (not all criteria must be present to be indicative of a Sponsor's product relationship).
Yes, there is a reasonable possibility of Sponsor's product relationship.	There is evidence of exposure to the Sponsor's product. The temporal sequence of the AE onset relative to the administration of the Sponsor's product is reasonable. The AE is more likely explained by the Sponsor's product than by another cause.
No, there is not a reasonable possibility of Sponsor's product relationship	Subject did not receive the Sponsor's product OR temporal sequence of the AE onset relative to administration of the Sponsor's product is not reasonable OR the AE is more likely explained by another cause than the Sponsor's product. (Also entered for a subject with overdose without an associated AE.)

7.2.5 Sponsor Responsibility for Reporting Adverse Events

All Adverse Events will be reported to regulatory authorities, IRB/IECs and investigators in accordance with all applicable global laws and regulations, i.e., per ICH Topic E6 (R1) Guidelines for Good Clinical Practice.

8.0 STATISTICAL ANALYSIS PLAN

This section outlines the statistical analysis strategy and procedures for the trial. Changes to analyses made after the protocol has been finalized, but prior to final database lock, will be documented in a supplemental statistical analysis plan and referenced in the Clinical Trial Report (CSR) for the trial. Post hoc exploratory analyses will be clearly identified in the CSR.

8.1 Statistical Analysis Plan Summary

Key elements of the statistical analysis plan are summarized in the Statistical Analysis Plan Summary below; the comprehensive plan is provided in Sections 8.2 to 8.12.

Unless indicated otherwise, statistical analyses will be performed separately for Dose Evaluation and Signal Detection of this trial. For Signal Detection, statistical analyses will be performed separately by cohort.

Statistical Analysis Plan Summary

Trial Design Overview	This trial, entitled “Phase Ib Trial of Pembrolizumab (MK-3475) in Combination with Dinaciclib (MK-7965) in Subjects with Hematologic Malignancies (KEYNOTE-155)” is a multicenter, multiple-cohort, non-randomized trial of dinaciclib (MK-7965) in combination with pembrolizumab (MK-3475) in subjects with relapsed or refractory CLL, MM, or DLBCL. After a Dose Evaluation phase, the cohorts (CLL, MM, DLBCL) will be enrolled for Signal Detection.
Treatment Assignment	In Dose Evaluation, 12 subjects (at least 3 subjects each with rrCLL, rrMM, or rrDLBCL) meeting inclusion/exclusion criteria will receive pembrolizumab and dinaciclib at the initial dose (Dose Level 0) as described in Table 3 and Table 11 ; Dose Levels -1 and -2 will be evaluated with no restriction on the distribution of disease types rrCLL, rrMM, and rrDLBCL. If and when the safety criteria for Dose Evaluation are met, Signal Detection will use the same doses of pembrolizumab and dinaciclib.
Analysis Populations	In Signal Detection, the primary analysis population for both efficacy and safety assessments is the “All Subjects as Treated” (ASaT) population, defined as all subjects who receive at least one dose of trial medication (pembrolizumab or dinaciclib).
Primary Endpoint(s)	The primary endpoint is DLT (as defined in Section 5.2.1.4).
Key Endpoints Secondary Endpoints	
 1. ORR according to investigator assessment using the overall population and for disease-specific criteria (as applicable) 2. DOR 3. PFS 4. OS
Statistical Methods for	In Signal Detection, the point estimate of the ORR will be calculated as well as

Key Efficacy Analyses	a 95% 2-sided exact confidence interval.
Statistical Methods for Key Safety Analyses	In Dose Evaluation, descriptive statistics will be used to evaluate the DLT rate. Summary statistics (counts, percentage, mean, standard deviation, etc.) will be provided for the safety endpoints as appropriate.
Interim Analyses	In Signal Detection, both safety and efficacy will be assessed prior to full enrollment within each cohort. In terms of efficacy, a cohort may terminate if inadequate efficacy is observed (0 responses out of first 12 evaluable subjects in the MM and DLBCL cohorts; 2 or fewer out of 12 for the CLL cohort); refer to Section 8.7 for details.
Multiplicity	No adjustment for multiplicity is planned.
Sample Size and Power	The minimum and maximum overall sample size for this trial is 102 and 131 subjects, respectively (ie, 12 to 41 from Dose Evaluation plus 90 from Signal Detection). Assuming a 5% non-evaluable rate (ie, not evaluable for DLT in Dose Evaluation or not treated in Signal Detection), a maximum of 138 subjects would be enrolled in this trial. In Signal Detection, with 30 subjects in the experimental arm (pembrolizumab + dinaciclib), the maximum half-width of the two-sided 95% confidence interval for ORR within each cohort is 19%.

8.2 Responsibility for Analyses/In-House Blinding

The statistical analysis of the data obtained from this trial will be the responsibility of the Clinical Biostatistics department of the Sponsor.

This trial is being conducted as an open-label trial; therefore, subjects, investigators, and Sponsor personnel will be aware of subject treatment assignments after each subject is enrolled and treatment is assigned.

8.3 Hypotheses/Estimation

No formal hypotheses are to be tested in this trial; objectives of the trial are stated in Section 3.

8.4 Analysis Endpoints

8.4.1 Efficacy Endpoints

Efficacy endpoints will be based on investigator assessment using the disease-specific criteria outlined in Section 7.1.2.8.

Primary

Objective Response Rate

ORR is defined as the proportion of subjects in the analysis population who achieved at least a partial response according to the disease-specific criteria (CR+PR for CLL and DLBCL; sCR+CR+VGPR (very good partial remission)+PR for MM).

Secondary

Duration of Response

For subjects who demonstrated a response (PR or better), DOR is defined as the time from first documented evidence of response until first documented evidence of disease progression or death due to any cause, whichever occurs first.

Progression-Free Survival

PFS is defined as the time from first dose of trial treatment to the first documented evidence of disease progression or death due to any cause, whichever occurs first.

Overall Survival

OS is defined as the time from first dose of trial treatment to death due to any cause.

8.4.2 Safety Endpoints

Safety measurements are described in Section 7.2.

8.5 Analysis Populations

In Dose Evaluation, subjects are considered to be evaluable for DLT assessment if the subjects meet all the following criteria:

- Subjects enrolled and received at least one dose of trial medication.
- Subject did not discontinue within the first 2 cycles, or subject experienced a DLT prior to completing the first 2 cycles of treatment

In Signal Detection, the analyses of efficacy and safety endpoints are based on the ASaT population. Subjects will be included if they receive at least 1 dose of trial medication.

At least 1 laboratory or vital sign measurement obtained subsequent to at least 1 dose of trial treatment is required for inclusion in the analysis of each specific parameter. To assess change from baseline, a baseline measurement is also required.

8.6 Statistical Methods

This section provides the statistical details for analyses of efficacy and safety endpoints.

A summary of the primary analysis strategy for the primary and secondary efficacy endpoints is provided in [Table 19](#).

The analyses will be performed for Signal Detection only, separately within each cohort. In Dose Evaluation, subject listings for these endpoints (ORR, DOR, PFS, and OS) will be provided.

8.6.1 Objective Response Rate

The analysis of ORR will consist of the point estimate and 95% 2-sided exact confidence interval using the Clopper-Pearson method, which will have at least 95% coverage of the true rate.

8.6.2 Duration of Response

The analysis of DOR will consist of Kaplan-Meier estimates. DOR data will be censored on the date of the last disease assessment documenting absence of progressive disease for subjects who do not have tumor progression and are still on trial at the time of an analysis, are given antitumor treatment other than the trial treatment, or are removed from trial prior to documentation of tumor progression.

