In the Signal Detection phase, approximately 30 subjects each with rrCLL, rrMM, or rrDLBCL will be enrolled in separate cohorts. The Dose Evaluation and Signal Detection phases will further evaluate safety and characterize preliminary efficacy.

In the Signal Detection phase, an interim analysis for safety and an efficacy interim analysis for futility will be conducted for each cohort after 12 subjects have been enrolled and the last subject has completed the first response assessment (ie, after Cycle 3 for CLL and rrDLBCL, and after Cycle 2 for rrMM), or otherwise discontinued trial treatment. Enrollment will be paused during the interim analysis (Section 8.7). The results will be reviewed by the trial

[figure not shown]
team. Enrollment may resume in that cohort if the results of the safety and efficacy analysis justify continuing.

Subjects will continue on treatment until disease progression (PD) (Section 7.1.2.7 and Section 7.1.2.8), unacceptable adverse event (AE), or treatment has been completed (ie, 35 cycles [approximately 2 years]). Subjects who discontinue treatment before PD, including subjects who discontinue treatment for bone marrow transplantation or to receive any other treatment, will be followed every 12 weeks for at least 12 months until PD is documented or until the end of the trial.

The primary objective of the trial is to evaluate the safety and tolerability of the combination of pembrolizumab and dinaciclib in subjects with hematologic malignancies. Secondary objectives by tumor type include the ORR, duration of response (DOR), progression-free survival (PFS), and overall survival (OS).

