8.6.3 Progression-Free Survival

The non-parametric Kaplan-Meier method will be used to estimate the PFS curve. Additional details, including censoring rules for those subjects without PD, are summarized in [Table 18](#).

Table 18 Censoring Rules for PFS

Situation	Analysis
No PD and no death; new anticancer treatment is not initiated	Censored at last disease assessment
No PD and no death; new anticancer treatment is initiated	Censored at last disease assessment before new anticancer treatment
PD or death documented after ≤ 1 missed disease assessment	Progressed at date of documented PD or death
PD or death documented after ≥ 2 missed disease assessments	Progressed at date of documented PD or death
No PD and no death and lost to follow-up after ≥ 2 missed disease assessments	Censored at last disease assessment

Abbreviation: PD = progressive disease.

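### Section 8.6.2 does not implement the DOR definition in 8.4.1: it makes no exception for death and does not limit the censoring date to assessments before other antitumor treatment

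*Combined protocol and SAP*

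**What the plan says.** Section 8.4.1 defines DOR as running from first documented response "until first documented evidence of disease progression or death due to any cause, whichever occurs first".

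Section 8.6.2 gives the only DOR censoring rule. DOR is "censored on the date of the last disease assessment documenting absence of progressive disease for subjects who do not have tumor progression" and who are still on trial at the analysis, "are given antitumor treatment other than the trial treatment, or are removed from trial prior to documentation of tumor progression". The rule therefore has three triggers and one censoring date, and death is not mentioned.

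PFS has its own rules under the title "Table 18 Censoring Rules for PFS". With neither progression nor death, a subject who starts new treatment is "Censored at last disease assessment before new anticancer treatment". Progression or death, whatever the number of missed assessments, is "Progressed at date of documented PD or death".

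Section 2.1 states that subjects who stop treatment before progression, "including subjects who discontinue treatment for bone marrow transplantation or to receive any other treatment, will be followed every 12 weeks"; it sets a minimum of 12 months. The Trial Summary (1.0), 5.5.2, flow chart footnote f, 7.1.1.5.4 and 7.1.5.4 instead end disease follow-up, or move the subject to survival follow-up, once new therapy starts. Section 5.5.2 also allows radiotherapy to certain lesions during treatment after consultation with the sponsor.

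**The concern.** A censoring rule should leave intact the events that the endpoint definition names. This one is built on tumor progression alone, so it can remove deaths in remission that 8.4.1 counts. It also takes other antitumor treatment as a reason to censor without saying that the censoring date must precede that treatment. Both gaps act in the same direction: they lengthen DOR, and part of the added time may belong to a transplant or to radiotherapy rather than to pembrolizumab plus dinaciclib. The same subject can also have a DOR that disagrees with his or her PFS.

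**Working it through.** **1. Plan figure.** There is none to reproduce. No sample size, interval width or futility rule depends on DOR censoring, and 8.3 states that no formal hypotheses are tested.

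**2. The rules applied to single records.** All dates are assumed, in weeks from first dose, with response at week 9. DOR = end date − 9. Record C assumes that transplant counts as new anticancer treatment; 7.1.1.5.4 collects transplant data under subsequent antineoplastic therapy.

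| Record | DOR event under 8.4.1 | DOR under 8.6.2 as written | PFS under Table 18 |
|---|---|---|---|
| A. Clean scan week 27; dies week 30 without progression; no other therapy | 30 − 9 = 21 | Censored at 27 − 9 = 18 if death is removal from trial; otherwise no trigger applies and the event at 21 stands | Event, week 30 |
| B. Clean scan week 18; other therapy week 20; dies week 30 without progression | 30 − 9 = 21 | Censored at 18 − 9 = 9 | Event, week 30 |
| C1. Clean scan week 18; transplant week 20; clean scans every 12 weeks as in 2.1 (32, 44, 56, 68) | None | Censored at 68 − 9 = 59 | Censored, week 18 |
| C2. As C1, but scans stop at new therapy (footnote f, 7.1.5.4) | None | Censored at 18 − 9 = 9 | Censored, week 18 |
| D. Clean scan week 18; lesion radiotherapy week 20, trial treatment continues; clean scans every 3 cycles (27, 36, 45) | None | Censored at 45 − 9 = 36 | Censored, week 18, if radiotherapy is new anticancer treatment; otherwise week 45 |

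Record B conflicts with 8.4.1 whatever removal from trial means. Its death is a PFS event because the new-treatment row of Table 18 covers only subjects with no progression and no death. In C1, DOR (59 weeks) exceeds the same subject's PFS time (18 weeks), although PFS starts earlier. Record D can show the same mismatch without relying on 2.1, because a subject still on treatment keeps the scheduled scans.

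**3. Sensitivity of the median.** Take 10 responders (the 10/30 example in Table 20). Assume progression at 9, 18, 27, 36 and 45 weeks of response and the other five censored at 60. Let 0 to 3 of those five instead die in remission at 14, 23 and 32 weeks, with last clean scans at 9, 18 and 27. The estimate is Kaplan-Meier, S(t) = Π(1 − d/n), and the median is the first time with S ≤ 0.5.

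With two deaths:
- Deaths as events: 9/10 × 8/9 × 7/8 × 6/7 × 5/6 = 0.50 at week 27, so the median is 27.
- Deaths censored at the last clean scan: 9/10 × 7/8 × 5/6 × 4/5 = 0.525 at week 36, then × 3/4 = 0.394 at week 45, so the median is 45.

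| Deaths in remission | Median, deaths as events | Median, deaths censored |
|---|---|---|
| 0 | 45 | 45 |
| 1 | 36 | 45 |
| 2 | 27 | 45 |
| 3 | 27 | 36 |

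With two deaths as events the curve stays at exactly 0.50 from week 27 to week 36. Software that reports the midpoint would give (27 + 36)/2 = 31.5, still well below 45.

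**The case against.** The strongest defence is that 8.4.1 and 8.6.2 can be read together. Section 8.4.1 fixes the events, and 8.6.2 only says what to do with subjects who have none. A responder who dies with no other therapy is not still on trial and received no other treatment, so only the removal trigger could apply. Elsewhere the protocol lists death separately from leaving the trial (1.0, 7.1.5.4.2), and 5.8.2 ties withdrawal from the trial to withdrawn consent. This stands as far as it goes: a reader might infer that every death in remission is censored, and the text does not say so. It does not help Record B, where the other-treatment trigger is met outright.

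A reader might also infer that transplanted responders keep accruing response time. That needs scans after the transplant. Section 2.1 provides for them, while five other places end disease follow-up at new therapy; if those govern, 8.6.2 and a limit like Table 18's give the same date (Record C2). The documents conflict here, so the inference is conditional. The radiotherapy route is narrower still, being an exception that needs sponsor consultation.

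Two further readings go too far. Section 8.6.2 does not contradict Table 18, which governs PFS only; the direct conflict is with 8.4.1, and the difference from Table 18 is an inconsistency between endpoints. Nor are toxic deaths hidden: they remain PFS and OS events and fall under serious adverse event reporting.

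**Conclusion.** The point holds in a limited form. Section 8.6.2 leaves death out of the DOR rule although 8.4.1 makes it an event, and it sets no limit on the censoring date once other treatment starts. The conflict with 8.4.1 is certain for a responder who dies without progression after other therapy. It depends on interpretation for one who dies with no other therapy. For scans after transplant it depends on which follow-up section is applied. For scans after radiotherapy, the mismatch with PFS depends on whether radiotherapy counts as new anticancer treatment.

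The size cannot be derived from the documents, because they do not say how many responders would die in remission or receive other therapy. The 27 versus 45 weeks rests on assumed event times and on both deaths being censored. It shows only that with about 10 responders one or two records can move the median. DOR is secondary and descriptive and futility rests on ORR, so no sample size, error rate or stopping rule changes. The correction is worth making because it is cheap and the DOR estimate is otherwise open to a programmer's choice.

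**What to change.** Rewrite 8.6.2 to state:

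- The event is first documented progression or death from any cause.
- Responders alive without progression and without other antitumor treatment are censored at the last disease assessment.
- Responders who start other antitumor treatment before progression are censored at the last assessment before that treatment, with a statement of whether transplant and radiotherapy count.

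Then state in both 8.6.2 and Table 18 the same handling of progression or death after new therapy. Editing 8.6.2 alone cannot align the two endpoints, because Table 18 now counts those as PFS events. If censoring before new therapy is to hold whatever follows, the new-treatment row of Table 18 must drop its restriction to subjects with no progression and no death, and 8.4.1 should refer to the rule. If later progression or death is to count, both endpoints must say so.

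Reconcile 2.1 with 1.0, 5.5.2, flow chart footnote f, 7.1.1.5.4 and 7.1.5.4 on whether disease assessment continues after new therapy.

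The cost is wording in 8.6.2 and Table 18, with a cross-reference in 8.4.1 if needed, plus the follow-up reconciliation. Section 8.0 allows changes before final database lock to be documented in a supplemental SAP. Reported DOR may be somewhat shorter, and PFS changes for subjects who progress or die after new therapy if Table 18 is amended in that direction.
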